#### **7.7 Rescue Medications, Treatments, and Procedures**

The ED setting and clinical staff are well-equipped to manage all potential adverse events associated with the study. Patients/Participants may receive treatment for other medical conditions and/or ancillary treatment for symptoms of opioid withdrawal (e.g., nausea, muscle aches) or sedation as clinically indicated in accordance with standard clinical practices. All medications, treatments, and procedures will be delivered as part of the clinical care of the ED visit.

### **8 Assessment of Safety**

#### **8.1 Specification of Safety Parameters**

### **8.1.1 Definition of Adverse Events (AE)**

An **adverse event** (AE) is any symptom, sign, illness or experience that develops or worsens in severity during the course of the study. Intercurrent illnesses or injuries should be regarded as adverse events.

Abnormal results of diagnostic procedures are considered to be adverse events if the abnormality:

- results in study withdrawal
- is associated with a serious adverse event
- is associated with clinical signs or symptoms
- leads to additional treatment or to further diagnostic tests
  - Note that the existing clinical protocol for the initiation of treatment with BUP in the Bellevue ED includes instructions for patients to return to the ED in some circumstances, including for repeat assessment, for social work or care management or referral assistance, for subsequent dose and/or prescription of BUP, for early return of withdrawal symptoms, etc. If return to the ED is for one of these reasons, it will not be considered an AE.
- is considered by the investigator to be of clinical significance

### **8.1.2 Definition of Serious Adverse Events (SAE)**

A **serious adverse event** (SAE) is any AE that results in any of the following outcomes:

- Death
- Life-threatening
- Event requiring inpatient hospitalization or prolongation of existing hospitalization
- Persistent or significant disability/incapacity
- Congenital anomaly/birth defect
- Based on the appropriate medical judgment, may jeopardize the participant's health and may require medical or surgical intervention to prevent one of the other outcomes listed in this definition.

### **8.1.3 Definition of Unanticipated Problems (UP)**

#### **Unanticipated Problems Involving Risk to Participants or Others**

Any incident, experience, or outcome that meets all of the following criteria:

- Unexpected in nature, severity, or frequency (i.e. not described in study-related documents such as the IRB-approved protocol or consent form, the investigators brochure, etc)
- Related or possibly related to participation in the research (i.e. possibly related means there is a reasonable possibility that the incident experience, or outcome may have been caused by the procedures involved in the research)
- Suggests that the research places participants or others at greater risk of harm (including physical, psychological, economic, or social harm).

## **8.2 Classification of an Adverse Event**

### **8.2.1 Severity of Event**

AEs are graded according to the following scale:

**Mild:** An experience that is transient, and requires no special treatment or intervention. The experience does not generally interfere with usual daily activities. This includes transient laboratory test alterations.

**Moderate:** An experience that is alleviated with simple therapeutic treatments. The experience impacts usual daily activities. Includes laboratory test alterations indicating injury, but without long-term risk.

**Severe:** An experience that requires therapeutic intervention and/or interrupts usual daily activities. If hospitalization (or prolongation of hospitalization) is required for treatment it becomes an SAE.

### **8.2.2 Relationship to Study Agent**

The study uses the following AE attribution scale:

Study Number: s19-01700

Version: 7.0

Version Date: 08/01/2022

**Not related:** The AE is clearly not related to the study procedures (i.e., another cause of the event is most plausible and/or a clinically plausible temporal sequence is inconsistent with the onset of the event).

**Possibly related:** An event that follows a reasonable temporal sequence from the initiation of study procedures, but that could readily have been produced by a number of other factors.

**Related:** The AE is clearly related to the study procedures.

### **8.2.3 Expectedness**

[name] will be responsible for determining whether an AE is expected or unexpected. An AE will be considered unexpected if the nature, severity, or frequency of the event is not consistent with the risk information previously described for the study agent.

## **8.3 Time Period and Frequency for Event Assessment and Follow-Up**

The occurrence of an AE or SAE may come to the attention of study personnel during study visits and interviews of a study participant presenting for medical care, or upon review by a study monitor. All AEs including local and systemic reactions not meeting the criteria for SAEs will be captured on the appropriate RF. Information to be collected includes event description, time of onset, clinician's assessment of severity, relationship to study product (assessed only by those with the training and authority to make a diagnosis), and time of resolution/stabilization of the event. All AEs occurring while on study must be documented appropriately regardless of relationship. All AEs will be followed to adequate resolution.

Any medical condition that is present at the time that the participant is screened will be considered as baseline and not reported as an AE. However, if the study participant's condition deteriorates at any time during the study, it will be recorded as an AE. UPs will be recorded in the data collection system throughout the study.

Changes in the severity of an AE will be documented to allow an assessment of the duration of the event at each level of severity to be performed. AEs characterized as intermittent require documentation of onset and duration of each episode.

The PI will record all reportable events with start dates occurring any time after informed consent is obtained until 7 (for non-serious AEs) or 30 days (for SAEs) after the last day of study participation. At each study visit, the investigator will inquire about the occurrence of AE/SAEs since the last visit. Events will be followed for outcome information until resolution or stabilization.

All unresolved adverse events should be followed by the investigator until the events are resolved, the participant is lost to follow-up, or the adverse event is otherwise explained. At the last scheduled visit (30 days), the investigator should instruct each participant to report any subsequent event(s) that the participant, or the participant's personal physician, believes might reasonably be related to participation in this study. The investigator should notify the study sponsor of any death or adverse event occurring at any time after a participant has discontinued or terminated study participation that may reasonably be related to this study. The sponsor should also be notified if the investigator should become aware of the development of cancer or of a congenital anomaly in a subsequently conceived offspring of a participant that has participated in this study.

## **8.4 Reporting Procedures – Notifying the IRB**

### **8.4.1 Adverse Event Reporting**

AEs are identified by the research coordinator or study team during study visits and phone call check-ins. After discharge, AEs are assessed at time of study follow-up visits.

All AEs and SAEs are reported according to the NYUSoM IRB's reporting guidelines.

The PI will report the following types of adverse events to the IRB and DSMB:

- a. Serious AND unanticipated AND possibly, probably or definitely related events;

Study Number: s19-01700

Version: 7.0

Version Date: 08/01/2022

- b. Anticipated adverse events occurring with a greater frequency than expected; and
- c. Other unanticipated problems involving risks to participants or others.

These adverse events or unanticipated problems involving risks to participants or others will be reported to the DSMB, IRB, and FDA (if required) within 72 hours of it becoming known to the investigator, using the appropriate forms. The PI and DSMB will conduct a review of all adverse events upon completion of every study participant. The PI will evaluate the frequency and severity of the adverse events and determine if modifications to the protocol or consent form are required.

#### **8.4.2 Serious Adverse Event Reporting**

See above Section 8.4.1.

#### **8.4.3 Unanticipated Problem Reporting**

Incidents or events that meet the OHRP criteria for UPs require the creation and completion of an UP report form. It is the site investigator's responsibility to report UPs to their IRB and to the study sponsor. The UP report will include the following information:

- Protocol identifying information: protocol title and number, PI's name, and the IRB project number;
- A detailed description of the event, incident, experience, or outcome;
- An explanation of the basis for determining that the event, incident, experience, or outcome represents an UP;
- A description of any changes to the protocol or other corrective actions that have been taken or are proposed in response to the UP.

To satisfy the requirement for prompt reporting, UPs will be reported using the following timeline:

- UPs that are SAEs will be reported to the IRB and to the study sponsor 72 hours of the investigator becoming aware of the event.
- Any other UP will be reported to the IRB and to the study sponsor within 72 hours of the investigator becoming aware of the problem.
- All UPs should be reported to appropriate institutional officials (as required by an institution's written reporting procedures), the supporting agency head (or designee), and OHRP within 72 hours of the IR's receipt of the report of the problem from the investigator.

#### **8.4.4 Reporting of Pregnancy**

As detailed previously, pregnant women will not be included in this study. If any of the study participants become pregnant, however, it will immediately be reported to ND or IDE sponsor, study leadership, IRB, and regulatory agencies. Pregnant patients will be managed with the help of experts, and on an individualized basis. OUD treatment can be continued throughout pregnancy, but patients must be aware of the risks to the fetus, both of continuing treatment and abruptly discontinuing treatment. Participants who become pregnant during the study will be retained in the study, unless they voluntarily remove themselves.

### **8.5 Reporting Procedures – Notifying the Study Sponsor**

The study clinician will complete a SAE Form within the following timelines:

- All deaths and immediately life-threatening events, whether related or unrelated, will be recorded on the SAE Form and submitted to the study sponsor within 24 hours of site awareness. See Section 1, Key Roles for contact information.
- Other SAEs regardless of relationship will be submitted to the study sponsor within 72 hours of site awareness.

All SAEs will be followed until satisfactory resolution or until the site investigator deems the event to be chronic or the adherence to be stable. Other supporting documentation of the event may be requested by the study sponsor and should be provided as soon as possible.

As a follow-up to the initial report, within the following 48 hours of awareness of the event, the investigator shall provide further information, as applicable, on the unanticipated event or the unanticipated problem in the form of a written narrative. This should include a copy of the completed Unanticipated Problem form, and any other diagnostic information that will assist the understanding of the event. Significant new information on ongoing unanticipated adverse effects shall be provided promptly to the study sponsor.

## **8.6 Study Halting Rules**

Administration of study agent will be halted when three grade 3 AEs determined to be "probably related" are reported to the sponsor. When the third grade 3 event is reported, enrollment screens will stop accepting new study participants. The study sponsor will inform the DSMB members within 24 hours of this occurrence and will provide the DSMB with AE listing reports. The DSMB will convene an ad hoc meeting by teleconference or in writing as soon as possible. The DSMB will provide recommendations for proceeding with the study to the study sponsor.

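### The only counted halting rule needs three events, so a first or second related death or life-threatening event triggers no automatic pause or DSMB meeting, and its attribution term is not on the protocol's scale

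*Combined protocol and SAP*

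**What the plan says.** Section 8.6 of the combined protocol and SAP sets the rule: "Administration of study agent will be halted when three grade 3 AEs determined to be" *probably related* have reached the sponsor. It continues: "When the third grade 3 event is reported, enrollment screens will stop accepting new study participants". The sponsor then tells the DSMB within 24 hours, and the DSMB holds an ad hoc review. All of this depends on the third event.

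The scales that should feed the rule come earlier. Section 8.2.1 says "AEs are graded according to the following scale" and lists Mild, Moderate and Severe, without numbers. Section 8.2.2 says "The study uses the following AE attribution scale" and lists Not related, Possibly related and Related. *Probably* appears elsewhere only in the reporting list of section 8.4.1: "Serious AND unanticipated AND possibly, probably or definitely related events".

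Other provisions cover serious events:
- **8.5:** "All deaths and immediately life-threatening events, whether related or unrelated, will be recorded on the SAE Form", which goes to the sponsor within 24 hours.
- **8.4.1:** events in the reporting list go to the DSMB and IRB within 72 hours. In addition, "The PI and DSMB will conduct a review of all adverse events upon completion of every study participant".
- **8.4.3:** unanticipated problems go to the IRB and sponsor within 72 hours.
- **8.7:** all adverse events go to the DSMB chair, and the principal investigator, DSMB or IRB may stop the study.
- **6.8:** the study may be suspended for unacceptable risk.
- **7.4.2:** the 24 mg dose is withheld from a participant who has a qualifying event after the first dose.

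**The concern.** A halting rule has to say which events count and how many are needed. This one is unclear on the first point. On the second, its threshold suits severe but recoverable events better than fatal ones.

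The 32 mg given on day 0 is four times the labeled induction maximum of 8 mg (32/8), although it lies within the approved maintenance range (section 2.1.4). The same section accepts that the higher dose may increase over-sedation. If a participant died or nearly died after the 24 mg dose and the event was judged related, staff who followed section 8.6 to the letter could go on dosing new participants until someone chose to stop. Recruitment may draw on five emergency departments (section 6.6), so a written trigger is more dependable than a decision improvised on the day.

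The undefined attribution level adds a smaller problem. Two clinicians could count the same events differently toward three.

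**Working it through.** The plan gives no operating characteristics for the halting rule, so there is no figure to reproduce. The check is mainly a comparison of sections, with arithmetic for scale.

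**1. Terms.** Section 8.2.1 has three ordered levels, so the third, Severe, is the natural meaning of *grade 3*. Nothing above Severe is defined, so a death has no level of its own. *Probably related* could mean Related only, or could reach down into Possibly related, which section 8.2.2 describes as an event in plausible time sequence "but that could readily have been produced by a number of other factors". No mapping is given.

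**2. Any other automatic trigger?**
- 7.4.2 acts on one participant, and only before the 24 mg dose.
- 8.5 and 8.4.3 require reports. Neither requires a pause.
- The first item in 8.4.1 requires the event to be serious, unanticipated and related. Over-sedation is a listed risk (2.1.4), so a life-threatening case might be classed as anticipated and miss that item.
- The per-participant review in 8.4.1 follows completion, not an event.
- 8.7 sets no deadline for reports to the DSMB chair. Beyond an annual meeting, the board meets when the study team thinks it necessary.
- 6.8 and 8.7 give authority to stop, without a count or an obligation.

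No section attaches a study-level pause to a first or second related death.

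**3. Exposure before a discretionary decision.** Inputs from section 6.5: 35 participants expected over 11 months, a target of 1 per week and a goal of 2 per week.
- 11 months = 11 × 365.25 / 12 / 7 = 47.8 weeks, and 35 / 47.8 = 0.73 per week.
- Further enrollees in 72 hours = rate × 3/7: 0.73 × 3/7 = 0.31; 1 × 3/7 = 0.43; 2 × 3/7 = 0.86.

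**4. How often the rule would stay silent.** The documents give no rate for related deaths or life-threatening events. In the chart review cited in section 2.1.3, none of 94 patients given 24 to 32 mg had an adverse event. The exact two-sided 95% upper bound is 1 − 0.025^(1/94) = 3.8%. With N = 35, at most one qualifying event per participant and assumed rates p, the chance of ending with exactly one or two events is P(≥1) − P(≥3):
- p = 1%: 0.297 − 0.005 = 0.291 (from unrounded values)
- p = 2%: 0.507 − 0.033 = 0.474

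**5. Cost of a single-event trigger.** The chance of at least one pause is 1 − (1 − p)^35:
- p = 0.5%: 0.161
- p = 1%: 0.297
- p = 2%: 0.507

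**6. Cost of widening the three-event rule.** If Possibly related events also count, p refers to a broader and probably commoner class. The chance of three or more in 35 is 0.254 at an assumed 5%, 0.694 at 10% and 0.981 at 20%.

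**The case against.** The strongest reply is that the plan does not lack oversight. A death reaches the sponsor within 24 hours. A serious, unanticipated, related event reaches the DSMB and IRB within 72 hours. Three separate parties can stop the study. The planners also give a reason for not expecting a safety stop: the drug is approved and earlier data raised no significant concern (8.7). On this view, automatic versus discretionary is a design preference, and nothing here touches the primary endpoint of a descriptive pilot.

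Most of that stands, and it limits the weight of the point. A reader might infer that a first death would go unreviewed, or that dosing would in fact continue after it. The documents support neither. They show only that no pause is required. A reader might also infer that the rule is unusable. That goes too far, because *grade 3* has a natural reading and only the attribution term is truly unmapped.

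It is tempting, too, to measure exposure over the 30 days to a participant's completion review. That does not fit a participant who dies, and an event meeting the first item in 8.4.1 reaches the DSMB within 72 hours.

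A single-event trigger does not remove judgment either, since someone must still attribute the event. What it removes is the further decision whether to pause once relatedness has been accepted.

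**Conclusion.** The point holds in a limited form. Section 8.6 needs three events on any reading, so a first or second related death or life-threatening event starts no mandatory pause, 24-hour DSMB notice or ad hoc meeting. *Probably related* has no counterpart in section 8.2.2, and the severity scale stops at Severe. The missing element is an obligation to pause, not review or authority.

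The size is modest: about 0.3 to 0.9 further participants enrolled and dosed in 72 hours, assuming enrollment at 0.73 to 2 per week and a report that takes the full window. Such events are probably rare, but their outcome may be irreversible. The rates behind the silence and pause probabilities are assumptions, and those figures are illustrative. The amendment is worth making because it is short and reuses an existing process.

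**What to change.** **Main change, in section 8.6.** Add that any single death or life-threatening SAE (as in 8.1.2) that begins after the first study buprenorphine dose pauses dosing and enrollment and starts the existing 24-hour DSMB notice and ad hoc review. The condition is attribution as Possibly related or Related for events beginning up to the day 3 visit, and Related for events beginning later. The stricter test after day 3 is meant to keep later overdoses with other likely causes from pausing the study. It also means that a later death judged only Possibly related would cause no pause, although the participant may then be taking the prescribed 16 mg daily. The day 3 boundary is a proposal and does not come from the documents; the sponsor may choose another.

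**Minor change.** Restate the three-event rule as Severe (8.2.1) plus a named level from 8.2.2. Related alone keeps the rule narrow. Including Possibly related broadens it and raises the chance of a halt, as step 6 of the working shows, and the amendment should acknowledge that.

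**Cost.** A few sentences by amendment, with no new committee or process. The downside is a short pause for an event the DSMB later judges unrelated. The 16%, 30% and 51% in step 5 are the chances of at least one pause of any kind, justified or not.

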## **8.7 Safety Oversight**

A Data and Safety Monitoring Board (DSMB) will be established for initial and ongoing protocol review, including data, protocol compliance, safety and efficacy data in compliance with the IRB.

[name], MD, and [name] will serve as the DSMB members for this study. [name] is an Emergency Department physician and a toxicologist, and [name] is a Psychiatrist and addiction researcher who has extensive experience in opiate research. Dr.'s [name] and [name] will ensure protocol compliance and data safety, and neither have ethical conflicts, including financial interest related to study outcome. If necessary, they will disclose any potential conflicts in writing. The board will meet at least annually, and as needed if a meeting is deemed necessary by the study team.

Day-to-day oversight of the trial is provided by the Principal Investigator (PI), [name]. [name] assures that informed consent is obtained prior to performing any research procedures, that all participants meet eligibility criteria, and that the study is conducted according to the IRB-approved research plan. [name] will review all study data and any adverse events (AEs) according to protocol, and report all AEs to the DSMB chair, sponsor, and IRB.

During DSMB board meetings, [name] and other research personnel will report on the trial status, followed by a closed session under the direction of the DSMB chairperson, during which time the investigators and research team may be present. This will be followed by an executive session restricted to DSMB members. Issues discussed may include those related to participant safety and benefit, whether the primary study question is being answered, conflict of interest, confidentiality, and ongoing study review (including AEs, SAEs, and regulatory issues). All adverse events and unanticipated problems during follow-up will be reported to the IRB, DSMB, and NIAAA. The PI will evaluate the frequency and severity of adverse events and determine if modifications to the protocol and/or consent form are required. During the review process, the DSMB will evaluate whether the study should continue unchanged, require modification/amendment, continue or close to enrollment. Either the principal investigator, DSMB, or the NYU IRB have the authority to stop or suspend the study or require modifications. Following the DSMB meeting, recommendations will be made by the chairperson to [name] and a final report (edited by all DSMB members) will be prepared and submitted to the NYU IRB. Stopping the trial due to safety concerns or interim analysis of the primary outcome are not anticipated; the study medication, BUP/NX, is FDA-approved, and no significant safety issues have arisen. DSM Plans typically include stopping rules that specify the outcome differences detected between groups during an interim analysis that can result in stopping the clinical trial. In general, stopping rules will reflect one of the following conditions: 1) there is clear evidence of harm or harmful side-effects of the treatment; 2) there is not likelihood of demonstrating treatment benefit; 3) there is overwhelming evidence of the benefit of the treatment. Again however, because we are simply using a higher dose of BUP/NX to initiate treatment, which is already FDA-approved for the indication in question, and since data from other studies do not suggest significant safety considerations, early stopping on the basis of clear benefit (yes/no) is not anticipated.

